### 4.2 Study Schematic

#### # There is not a randomization procedure

§ Allowed CCBs at screening: Felodipine, isradipine, lacidipine, lercanidipine, nicardipine, nifedipine, and nisoldipine. Patients treated with Amlodipine 10 mg or Zofenopril other than 30 mg will not undergo screening procedures.

Grade 1-2 hypertensive patients: Blood pressure (BP) ranging from  $\geq$  140/90 mmHg to  $\leq$  179/109 mmHg

Uncontrolled patients with grade 1-2 hypertension: Sitting SBP/DBP > 130/80 mmHg. Patients with Grade 3 (SBP  $\ge$  180 or DBP  $\ge$  110 mHg) hypertension will be withdrawn from the study at Visit 2 and Visit 3.

Controlled patients: SBP/DBP ≤ 130/80 mmHg

### 4.3 Schedule of Assessments

	VISIT 1 / WEEK -4	VISIT 2 / WEEK 0± 2 days	VISIT 3 / WEEK 4± 2 days	VISIT 4 / WEEK 8± 2 days
Informed consent submitted	~			
IWRS f registration	~	1	~	~
Inclusion/exclusion criteria	~			
Medical history	~			
Prior medications	~	5		
Demographic information	~			
Concurrent diseases and medical conditions	~	~	~	1
Monotherapy of ZOF 30 mg or AML 5 mg dispensing a	~			
Extemporaneous combination of ZOF/AML 30/5 mg dispensing		~	√b	
Extemporaneous combination of ZOF/AML 30/10 mg dispensing			10	
Study drug return/accounting (Compliance assessment)		~	~	√
Concomitant medications	1	1	1	1
Urine Pregnancy test	~	1	1	~
Physical examination	~	1	1	~
Vital signs	~	1	1	1
Laboratory tests d	~			~
Blood pressure assessment	~	~	1	✓
ECG	~			~
AE/SAE assessment e	~	1	~	~
BP device provided to patientsh	×			
Patient diary provided to patients g	~	1	1	
Patient diary to be returned by patient if used g			~	~
BP device returned to site i				~

a. Patients on ZOF 30 mg or AML 5 mg will continue the same therapy for 4 weeks. Patients on any other ACE-i will be assigned to monotherapy with ZOF 30 mg and the patients on other CCBs (the allowed CCBs

are: felodipine, isradipine, lacidipine, lercanidipine, nicardipine, nifedipine, and nisoldipine) will be assigned to monotherapy with AML 5 mg

- b. Only patients controlled at Visit 3 will receive ZOF/AML 30/5 mg
- c. Only patients uncontrolled at Visit 3 will receive ZOF/AML 30/10 mg.

d. To ensure patient safety, the patients will be contacted over phone within 24 hours, in case of any abnormality and clinically relevant laboratory test according to the Investigator's judgement at any visit e. The Investigator is expected to also record any AE which was ongoing at the last treatment dose and a follow-up phone call should be made after 2 weeks from the last study visit.

In case AE was ongoing, the Investigator is expected to follow-up until the outcome of the AE has been determined.

- f. IWRS- Interactive Web Response System
- g. The following procedure is applied only in case of COVID-19 restrictions.

h. Patients will be provided with an automatic blood pressure device to be used in case they are not able to go to the study centre due to Covid-19 pandemic situation.

i. The patient will return the device at the last visit at the site

### 4.4 Inclusion-Exclusion Criteria and General Study Population

### 4.4.1 Inclusion Criteria

A patient will be considered eligible for inclusion in the study only if all the following criteria are met:

- Male or female Grade 1-2 hypertensive patients: with mean sitting SBP ≥140 mmHg and ≤179 mmHg and/or mean sitting DBP ≥ 90 mmHg and ≤109 mmHg at Screening, with ≥18 and ≤65 years of age, on monotherapy either with ZOF 30 mg or AML 5mg or any other ACE-I or CCBs (Felodipine, isradipine, lacidipine, lercanidipine, nicardipine, nifedipine, and nisoldipine) for at least 1 month before Visit 1 (Screening).
- 2. Patients who are able to understand and give written informed consent at Screening
- 3. Patients who are available for the entire trial period and willing to adhere to the protocol requirements
- 4. Ability to take oral medication and willing to adhere to the drug regimen
- 5. Female patients are eligible to participate if not pregnant, or not breastfeeding and must refrain from donating or storing eggs. For females of reproductive potential: use of highly effective contraception (e.g., method of birth control throughout the study period and for 4 weeks after study completion defined as a method which results in a failure rate of less than 1% per year) such as:
  - a. Combined (estrogen- and progestogen-containing) hormonal contraception associated with inhibition of ovulation (oral, intravaginal, transdermal)
  - b. Progestogen-only hormonal contraception associated with inhibition of ovulation (oral, injectable, implantable)
  - c. Intrauterine device (IUD)
  - d. Intrauterine hormone-releasing system (IUS)
  - e. Bilateral tubal occlusion
  - f. Vasectomized partner (performed at least 2 months before screening) (if the partner is the sole sexual partner of the trial participant and that the vasectomized partner has received medical assessment of the surgical success)
- 6. A male patient must agree to use contraception during the whole study period and for at least 1 week after the last dose of study treatment and refrain from donating sperms during this period

### 4.4.2 Exclusion Criteria

Any patient who meets any of the following criteria will not qualify for entry into the study:

- Known contraindications, presence of not recommended/contraindicated concomitant therapy allergies, or significant history of hypersensitivity to zofenopril, amlodipine, other ACE-inhibitors or dihydropyridines, or any related products (including excipients of the formulations as outlined in the Investigator's Brochure [IB]), or summary of product characteristics (SmPCs) or local package inserts for AML and ZOF
- Patients with serious disorders (in the opinion of the Investigator) which may limit the ability to evaluate the efficacy or safety of the tested medications, including cerebrovascular, cardiovascular, renal, respiratory, hepatic, gastrointestinal, endocrine/ or metabolic, haematological, or oncological, neurological, and psychiatric diseases. The same applies for immunocompromised and/or neutropenic patients
- 3. Patients having a history of the following within the last 6 months: myocardial infarction, unstable angina pectoris, percutaneous coronary intervention, bypass surgery, valve replacement (transcatheter aortic valve implantation, mitraclip), cerebrovascular accident (stroke, heart failure, hypertensive encephalopathy, cerebrovascular accident (stroke), or transient ischemic attack. Patients with who have undergone other surgery that in the in the opinion of the Investigator may limit the ability to evaluate the efficacy or safety of the tested medications.
- Patients with secondary hypertension of any aetiology such as renal diseases, pheochromocytoma, Cushing's syndrome hyperaldosteronism, renovascular disease, thyroid disorders
- 5. Patients with severe heart failure (New York Heart Association classification III-IV), a narrowing of the aortic or bicuspid valve, an obstruction of cardiac outflow (obstructive, hypertrophic cardiomyopathy) or symptomatic coronary disease
- 6. Patients with clinical evidence of renal disease as per the Investigator's judgement (including renovascular occlusive disease, nephrectomy and/or renal transplant, bilateral renal artery stenosis or unilateral renal artery stenosis in a solitary kidney, or severe renal impairment)
- 7. Patients with history of angioneurotic oedema
- 8. Patients with clinically relevant hepatic impairment
- 9. Patients with sick sinus syndrome, including sino-atrial block
- 10. Patients with second- or third-degree heart block (without a pacemaker)
- 11. Participation in any other interventional drug trial or exposure to other investigational agents within 30 days before Screening (Visit 1)
- 12. Inability to cooperate or any condition that, in the opinion of the Investigator, could increase the patient's risk of participating in the study or confound the outcome of the study
- 13. Patients with conditions that, in the opinion of the Investigator, would prevent a careful adherence to the protocol
- 14. Patients with severe hypotension
- 15. Patients who suffer from shock (including cardiogenic shock)
- 16. Patients treated with Amlodipine 10 mg and Zofenopril (other than 30 mg)

### 4.5 Randomization and Blinding

This is a non-randomized, unblinded study.

### 4.6 Sample Size

A total sample size of 216 patients is required to achieve 90% power at a 5% significance level

assuming a difference in mean DBP from baseline (Visit 2) to 8 weeks (Visit 4) of 4 mmHg and a standard deviation (SD) for this difference of 10 mmHg. The mean change in DBP for the null hypothesis is set equal to 2 mmHg. The alternative hypothesis is that the mean change in DBP is greater than 2 mmHg. To achieve this sample size, a total of 290 patients will be enrolled, allowing for a 25% withdrawal rate.

### 5 General Considerations

### 5.1 Timing of Analyses

No interim analysis is planned for this study. The final analysis will be performed after finalization and approval of this Statistical Analysis Plan (SAP) and after database lock.

### 5.2 Study Variables

### 5.2.1 Baseline

Patients are instructed to take the study treatment after all visit evaluations have been performed on scheduled visit days. Assessments performed at Visit 2 will be considered Baseline since the first dose combination therapy (ZOF/AML) occurs after the completion of Visit 2 assessments. For assessments performed at Visit 1 and not Visit 2 (e.g., laboratory and ECG assessments), the Visit 1 assessment will be considered Baseline.

### 5.2.2 First Dose

First dose is defined as the first administration of the extemporaneous combination of ZOF 30 mg and AML 5 mg that occurs on Visit 2 (Baseline). Monotherapies taken prior to Visit 2 should not be considered when defining first dose.

### 5.2.3 Study Day

Study Day of assessments or events is relative to first study drug dose date and is calculated as:

- (Date of assessment date of first dose + 1) if date of assessment  $\geq$  date of first dose.
- (Date of assessment date of first dose) if date of assessment < date of first dose.

#### 5.2.4 Visit Windows

It is expected that all visits should occur according to the protocol schedule. All visit data will be tabulated per the evaluation visit as recorded in the Electronic Case Report Form (eCRF), even if the assessment is outside of the visit window. Early termination visits will be presented in both summary tables and data listings, but unscheduled visits will be presented in the data listings only.

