2.2 Study Flow Chart

The assessment schedule lists all the assessments and when they are performed. All data obtained from these assessments mut be supported in the subject's source documentation. Subjects who prematurely discontinued the study for any reason should be scheduled for a visit as soon as possible. All the assessments listed for the final visit (Visit 4) will be performed. At this final visit, all dispensed investigational treatment should be reconciled, and the adverse events and concomitant medications recorded in the eCRF.

Informed consent must be signed prior to any study-related procedure.

MENARINI	Corporate Medical Department			
Identification Number	Version Number	State	Effective date	
FORM-000050125	2.0, CURRENT	Effective	08, Jan 2021	

	VISIT 1 / WEEK -4	VISIT 2 / WEEK 0± 2 days	VISIT 3 / WEEK 4± 2 days	VISIT 4 / WEEK 8± 2 days
Informed consent submitted	✓	·		
IWRS ^f registration	✓	✓	✓	✓
Inclusion/exclusion criteria	✓			
Medical history	✓			
Prior medications	✓			
Demographic information (for more details see section 8)	*			
Concurrent diseases and medical conditions	✓	✓	✓	✓
Monotherapy of ZOF 30 mg or AML 5 mg dispensing ^a	✓			
Extemporaneous combination of ZOF/AML 30/5 mg dispensing		✓	√b	
Extemporaneous combination of ZOF/AML 30/10 mg dispensing			√c	
Study drug return/accounting (Compliance assessment)		✓	✓	✓
Concomitant medications	✓	✓	✓	✓
Urine Pregnancy test	✓	✓	✓	✓
Physical examination (for more details see section 8)	✓	✓	✓	✓
Vital signs (for more details see section 8)	✓	✓	✓	✓
Laboratory tests ^d	✓			✓
Blood pressure assessment	✓	✓	✓	✓
ECG	✓			✓
AE/SAE assessment ^e	✓	✓	✓	✓

МЕМАЯНИ	Согр	porate Medical Departmo	ent
Identification Number	Version Number	State	Effective date
FORM-000050125	2.0, CURRENT	Effective	08, Jan 2021

Sponsor: Menarini International Operations Luxembourg SA Study Code: MEIN/20/ZoAm-Hyp/001	Protocol Version 1.0 of 1	23/04/2021	
Simily Could highly 20/20/1m Hyp/001			

BP device provided to patientsh	✓			
Patient diary provided to patients ^g	✓	✓	✓	
Patient diary to be returned by patient if used ^g			*	✓
BP device returned to site ⁱ				✓

- a. Patients on ZOF 30 mg or AML 5 mg will continue the same therapy for 4 weeks. Patients on any other ACE-i will be assigned to monotherapy with ZOF 30 mg and the patients on other CCBs (the allowed CCBs are: felodipine, isradipine, lacidipine, lercanidipine, nicardipine, nifedipine, and nisoldipine) will be assigned to monotherapy with AML 5 mg

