- Patients with abnormal renal function (creatinine clearance <30 mL/min) and/or abnormal liver enzyme parameters (alanine aminotransferase [ALT] or aspartate aminotransferase [AST] level of >2.5 × upper limit of normal [ULN] or total bilirubin level >1.5 × ULN).

If a patient has been withdrawn due to an AE, the Investigator must immediately contact the relevant pharmacovigilance contact (see Safety Data Management section). The reason for patient withdrawal must be well-documented in the Electronic Case Report Form (eCRF). The eCRF should capture the date and specific underlying reason for discontinuation of study product or patient discontinuation/withdrawal. Study treatment must be discontinued, and no further assessment conducted, and the data that would have been collected at subsequent visit will be considered missing. Further attempts to contact the patient are not allowed unless safety findings require communication or follow-up. All effort should be made to complete the assessment prior to study withdrawal. A final evaluation at the time of the patient's study withdrawal should be made as detailed in Early termination visit scheduled assessment.

Patients who discontinue from the study early will complete an early termination visit.

MENARINI	Corporate Medical Department		
	** * ** *	G	77.00 dt 1
Identification Number	Version Number	State	Effective date
FORM-000050125	2.0, CURRENT	Effective	08, Jan 2021

Subjects who prematurely withdrawn from study medication or from the study will not be replaced. These subjects will not be considered lost to follow-up.

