### 5.3.3 Efficacy Population (EFF)

The Efficacy Population (EFF) is defined as all study participants in the Safety Population who complete the 4-week run-in period and meet continuation criteria at Visit 2 [uncontrolled BP (sitting SBP/DBP > 130/80 mmHg), tolerate treatment, and fall within 80-120% treatment adherence] and have at least one available post baseline primary efficacy assessment (from Visit 3 or 4). This population will be used for efficacy analyses.

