### 8.2 Adverse Events, Adverse Drug Reactions, and Deaths

Adverse Events (AEs) are any untoward medical occurrence in a clinical trial patient administered a medicinal product and which does not necessarily have a causal relationship with this treatment.

*Treatment Emergent AEs (TEAEs)* are defined as AEs that occur only once treatment has started (after the first dose of monotherapy of ZOF or AML). Thus, all AEs that occur in both the monotherapy and combined therapy periods will be considered treatment-emergent.

Adverse Drug Reactions (ADRs) are defined as AEs that have a relationship of "certain," "probable," "possible," or "unassessable."

All AEs will be coded using the Medical Dictionary for Regulatory Activities (MedDRA) version 24.1 or later.

The following tabulations will be produced for the monotherapy period and the combination therapy periods for the SAF population:

- Monotherapy Period (Day of Visit 1 through day before Day of Visit 2)
  - All treatment-emergent AEs (TEAEs)

- Severe TEAEs
- Adverse Drug Reactions (ADRs)
- TEAEs leading to study discontinuation
- Serious TEAEs (TESAEs)
- o Serious ADRs
- TESAEs with outcome of death
- Combination Therapy Period (Day of Visit 2 through Day of Visit 4)
  - All treatment-emergent AEs (TEAEs)
  - Severe TEAEs
  - Adverse Drug Reactions (ADRs)
  - TEAEs leading to study discontinuation
  - Serious TEAEs (TESAEs)
  - Serious ADRs
  - TESAEs with outcome of death

Key guidelines for counting incidence proportions of AEs/TEAEs/ADRs (collectively referred to as AEs for the remainder of this section) are as follows:

- When a patient has the same AE reported multiple times during an analysis period based on MedDRA terminology (SOC or PT), the patient will only be counted once within a level of MedDRA in an AE incidence table.
- When assessing investigator reported relationship to study drug of the AEs, if an AE reported multiple times changes in causal relationship during an analysis period for a patient, the event with highest relatedness will be presented. Related AEs (i.e., ADRs) will include those reported as "certain," "probable," "possible," or "unassessable" by the investigator.

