### 8.3 Clinical Laboratory Evaluations

For laboratory safety continuous variables, values recorded as "<X" or " $\leq$ X" or " $\geq$ Y" or " $\geq$ Y" will be imputed by "X" and "Y" respectively for descriptive statistics. This will be documented in a footnote in all output where such a replacement was performed. Continuous clinical laboratory observed values and change from Baseline (Visit 1) to Visit 4 will be summarized by combined therapy group (ZOF/AML 30/5 mg or ZOF/AML 30/10 mg) and overall for the SAF population.

Each laboratory result will be classified as Normal, Abnormal Not Clinically Significant (NCS), or Abnormal Clinically Significant (CS) at each visit. Shift tables from Baseline (Visit 1) to Visit 4 will be provided for each laboratory parameter, summarized by combined therapy group (ZOF/AML 30/5 mg or ZOF/AML 30/10 mg) and overall for the SAF population. If a patient has a missing lab parameter value at Visit 1 or Visit 4, that patient will be excluded from the shift analysis for that lab parameter but will be included in the corresponding by-patient data listing.

All laboratory parameters will also be presented in by-patient data listings for the SAF population.

Test	Visit	Laboratory Parameters to be Analyzed
		Red blood cell
		White blood cell
		Haemoglobin
		Haematocrit
		Platelets
		Neutrophils
		Lymphocytes
Haematology	Screening (Visit 1) and Visit 4	Monocytes
		Eosinophils
		Basophils
		Neutrophils absolute
		Lymphocytes absolute
		Monocytes absolute
		Eosinophils absolute
		Basophils absolute
		ALT
		Albumin
		Alkaline phosphatase
		AST
		Direct bilirubin
		Total bilirubin
		Total protein
		Creatinine
		Blood urea nitrogen
Serum Chemistry	Screening (Visit 1) and Visit 4	Creatine kinase
		GGT
		Triglycerides
		Cholesterol
		High- and low-density lipoprotein
		Chloride
		eGFR
		Blood glucose
		Potassium
		Uric acid

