### 8.6.2 ECG Variable Analyses

Continuous ECG observed values and change from Baseline (Visit 1) to Visit 4, as well as the number and % of patients in each Rhythm category (Sinusal or Other), will be summarized by combined therapy group (ZOF/AML 30/5 mg or ZOF/AML 30/10 mg) and overall for the SAF population.

ECG Interpretations will be classified as Normal, Abnormal Not Clinically Significant (NCS), or Abnormal Clinically Significant (CS) at each visit. Shift tables from Baseline (Visit 1) to Visit 4 will be provided the EDC Interpretations, summarized by combined therapy group (ZOF/AML 30/5 mg or ZOF/AML 30/10 mg) and overall for the SAF population. If a patient has a missing ECG Interpretation at Visit 1 or Visit 4, that patient will be excluded from the shift analysis but will be included in the corresponding by-patient data listing.

All ECG parameters, including individual results from all 3 measurements at each visit, as well as the final result used in the summary tables, will be presented in a by-patient data listing for the SAF population.

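### Laboratory and ECG results of patients who stop the combination before Visit 4 have no place in the change and shift tables unless the eCRF files them under Visit 4, and the EFF definition drops those who stop before Visit 3

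*SAP*

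**What the plan says.** **Collection.** Protocol 2.2 states "Subjects who prematurely discontinued the study for any reason should be scheduled for a visit as soon as possible", and asks for every Visit 4 assessment at that visit. Its flow chart schedules laboratory tests and ECG at Visits 1 and 4 only. Protocol 10 states "Study treatment must be discontinued, and no further assessment conducted, and the data that would have been collected at subsequent visit" are to count as missing, and rules out further contact unless safety findings call for it. The same section also asks for a final evaluation at withdrawal and an early-termination (ET) visit.

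**Tabulation.** SAP 5.2.4 promises: "Early termination visits will be presented in both summary tables and data listings, but unscheduled visits will be presented in the data listings only". It also says "All visit data will be tabulated per the evaluation visit as recorded in the Electronic Case Report Form (eCRF"). SAP 8.3 summarises laboratory values at Visit 1 and Visit 4 and adds: "If a patient has a missing lab parameter value at Visit 1 or Visit 4, that patient will be excluded from the shift analysis". SAP 8.6.2 has the same rule for ECG: "If a patient has a missing ECG Interpretation at Visit 1 or Visit 4, that patient will be excluded from the shift analysis". Both sentences go on to keep the patient in the by-patient listing.

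**Efficacy population.** SAP 5.3.3 requires EFF patients to "have at least one available post baseline primary efficacy assessment (from Visit 3 or 4"). The LOCF sensitivity analysis (SAP 5.6.1, 7.2.2; Table 14.2.2.3) is run on EFF. Protocol 12.3 asked only for completion of the run-in and a Visit 2 BP assessment. SAP 10.1 describes the change to EFF as the addition of the Visit 2 continuation criteria, and nothing else.

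**The concern.** Laboratory tests and ECG are scheduled once after treatment starts, at Visit 4. For a patient who takes the combination and stops earlier, the ET sample is therefore the only post-treatment result that the protocol calls for. Patients who stop for intolerance, an adverse event, or a renal or liver abnormality are plausibly those whose results matter most. A change or shift table restricted to patients with Visit 4 data describes those who stayed, and SAP 5.2.4 tells the reader otherwise.

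For efficacy, LOCF is the only missing-data analysis planned. A population rule that removes the earliest stoppers before LOCF is applied limits what that analysis can show, and the rule does not appear in the SAP's own list of changes to the protocol.

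**Working it through.** **1. The plan's own figure.** The counts below start from 216.
- Inputs (Protocol 12.2, SAP 4.6): change 4 mmHg, null 2 mmHg, SD 10 mmHg, power 90%, level 5%. SAP 4.6 gives a directional alternative.
- n = ((1.645 + 1.282) × 10 / 2)² = 214.1 by the normal approximation. The exact t calculation gives 216, with power 90.1%. The figure reproduces as a one-sided test.
- 216 / 0.75 = 288, consistent with 290 enrolled.
- Protocol 5 makes 216 the number who start the assessment period. No loss after Visit 2 is stated.

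**2. Collection passages side by side.** Protocol 2.2 schedules a visit after discontinuation with all Visit 4 assessments. Protocol 10 excludes further assessment and most contact, yet also requires an ET visit. The flow chart has no ET column. A site could follow either section and believe that it complied.

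**3. Promise against shells.**
- Laboratory change and shift (Tables 14.3.4.1.1, 14.3.4.1.2, 14.3.4.2.1, 14.3.4.2.2): Visit 1 and Visit 4 only.
- ECG change and shift (Tables 14.3.8.1, 14.3.8.2): Visit 1 and Visit 4 only.
- BP by visit, vital signs and physical examination (Tables 14.2.1.x, 14.3.6.2, 14.3.7.2): Visits 3 and 4 after baseline. These at least hold a Visit 3 value for anyone who reached it.
- No summary shell has an ET row, and no rule maps an ET visit to a numbered visit.

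**4. Number affected.** Assumed share of the 216 stopping before Visit 4, with the number remaining rounded down:
- 5%: 216 × 0.95 = 205.2, so 205 remain and 11 have no Visit 4 value.
- 10%: 216 × 0.90 = 194.4, so 194 remain and 22 have none.
- 20%: 216 × 0.80 = 172.8, so 172 remain and 44 have none.

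For illustration only, suppose that 3 of 22 stoppers had a new clinically significant value and no completer did. The shift table would show 0/194, where a last-value shift would show 3/216 = 1.4%.

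**5. EFF and LOCF.** A patient with a Visit 3 BP is in EFF and is carried forward; only those who stop before Visit 3 are lost. At 10% loss (22 patients), 0, 11 or 22 are lost if none, half or all stop before Visit 3. The shells disagree on the definition: Table 14.1.2 uses the SAP wording of EFF, while Listing 16.2.3 still carries the protocol's.

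Size: if a share p stops before Visit 3 with no DBP change and the rest fall by 4 mmHg, the mean with everyone included is 4(1 − p). Leaving the stoppers out overstates it by 4p. For p = 0.05 to 0.10 that is 0.2 to 0.4 mmHg. The SE is 10/√216 = 0.68 mmHg.

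**6. Primary test.** For the planned two-sided test against 0 mmHg (SAP 7.2.1), with a true change of 4 mmHg and SD 10, power stays above 99.9% with 205, 194 or 172 patients.

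**The case against.** The strongest reply is that early stoppers do not vanish from the safety output. They stay in the Visit 1 rows, the listings, the AE tables and the disposition table. Protocol 9.9 makes a clinically relevant new or worsening laboratory abnormality an AE, so such values should reach the TEAE tables. Table 14.1.1 has discontinuation rows for adverse events and for abnormal renal function or liver enzymes. A reader might infer that stoppers are missing from Endpoint 2.5 as a whole; the documents do not support that. What remains is narrower: the laboratory and ECG change and shift tables.

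A reader might also infer that AEs are lost because the window is the "Combination Therapy Period (Day of Visit 2 through Day of Visit 4"). Without a Visit 4 the upper end is undefined, but no text drops an event. TEAEs have no end date in SAP 8.2, and Listing 16.2.7.1 assigns each AE to a period.

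The loss is also conditional. Protocol 2.2 describes the stopping assessments as those of Visit 4, and the SAP tabulates by the visit recorded in the eCRF. If the eCRF labels them Visit 4, they enter the tables. That stands, but the documents do not say so. It would also raise another problem: the Safety population includes run-in withdrawals who never took the combination, and their ET values could then enter the All Patients Visit 4 rows. A written rule is needed either way.

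Protocol 10 can be read more mildly as evaluating the patient at withdrawal and doing nothing afterwards. That makes the section more coherent, but Protocol 2.2 still schedules a visit after discontinuation, against the limit on contact.

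On LOCF, it is tempting to say that early stoppers in general drop out. They do not: those withdrawn at Visit 3 with a BP reading are retained. Protocol 12.3 also limits each analysis to patients with available data, so its wider population would not by itself have supplied a value for a patient with none. It would not have excluded a patient with an ET BP.

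**Conclusion.** The point holds in a limited form. The SAP promises ET data in summary tables, and its laboratory and ECG sections then leave such data out, with an explicit exclusion from the shifts. The result is completers-only post-treatment laboratory and ECG tables, unless the eCRF files ET visits as Visit 4. The protocol conflict over assessment at withdrawal is real and must be reconciled. The added EFF condition removes only patients who stop before Visit 3, and SAP 10.1 does not report it.

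The size rests on assumptions. The documents give no dropout rate for the assessment period, so 11 to 44 patients is a range for 5% to 20% loss, and the 1.4% is an invented example. The LOCF shift of 0.2 to 0.4 mmHg assumes 5% to 10% stopping before Visit 3 with no change, and is below one SE. The primary DBP conclusion is not at risk. The change should be made for safety reporting and for an accurate record of the analysis population.

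**What to change.** 1. Reconcile Protocol 2.2 and Protocol 10 into one rule on what is assessed at withdrawal.
2. In Tables 14.3.4.1.x, 14.3.4.2.x, 14.3.8.1 and 14.3.8.2, add an ET row and base the shifts on Visit 1 to the last post-baseline value (Visit 4 or ET), for patients with at least one combination dose. Show ET values of run-in withdrawals separately, as monotherapy data.
3. In SAP 5.3.3 and 5.6.1, let an ET BP taken after the first combination dose count as a post-baseline value for EFF entry and as the last observation for LOCF. Record the full EFF change in SAP 10.1 and align Listing 16.2.3 with it. Carrying the Visit 2 value forward for patients with no later BP is optional.

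The cost is a protocol clarification, SAP wording and some table rows, all of which can be settled before database lock. The tables need no visit or procedure beyond what Protocol 2.2 already asks for; if the reconciled rule collects less, the ET rows hold fewer values. The one drawback is that last-value rows mix durations of exposure, which a footnote can state.
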